## 2.3 Secondary Objectives and Endpoints

Secondary Objective	Endpoints	Time Frame
1. To determine safety of the combination of apalutamide and cetrorelimab	
 
Proportion of participants with treatment-related AEs, as graded by National Cancer Institute Common Terminology Criteria for Adverse Events (NCI CTCAE version 5.0)
 
	From initiation of study treatment until treatment discontinuation.
2. To determine the median radiographic progression-free survival by PCWG3 criteria	
 
Median progression free survival by PCWG3 criteria.
 
	From initiation of study treatment until radiographic progression by PCWG3 criteria or death, whichever occurs first.
3. To determine the PSA50 and PSA90 response proportion.	
 
<math>\geq 50\%</math> and <math>\geq 90\%</math> decline from baseline in PSA, respectively, confirmed by repeat measurement <math>\geq 4</math> weeks after first time point*
 
	From initiation of study treatment until maximal decline in serum PSA during study treatment.
4. To determine the median PSA progression-free survival.	
 
Median PSA progression-free survival by PCWG3 criteria.
 
	From initiation of study treatment until PSA progression by PCWG3 criteria or death, whichever occurs first.
5. To determine the median overall survival.	
 
Median overall survival from date of start of protocol treatment until death from any cause.
 
	From initiation of study treatment until death from any cause. (3 years)
6. To determine the objective response rate by RECIST 1.1 criteria	
 
Objective response rate by RECIST 1.1 criteria.
 
Median duration of response
 
	From initiation of study treatment until maximal percent decline from baseline in SLD of target lesions.

\* To be considered evaluable for this endpoint, patients must have baseline PSA level  $> 2$  ng/mL.

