Duration of Follow Up	Safety Follow up: 30 days Safety Follow-up: 100 days  Long Term / Survival Follow up: Patients will be followed for overall survival every 90 days (+/- 30 days) from last dose of study treatment, until death, withdrawal of consent, or the end of the study, whichever occurs first.

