### **3.6 Criteria for Study Discontinuation**

Participants will have safety follow up assessment 30 (+/- 7 days) and 100 days (+/- 14 days) following End of Treatment.

Following completion of safety follow up visits, patients will subsequently be followed for overall survival every 90 days (+/- 30 days) until death, withdrawal of consent, or the end of the study, whichever occurs first.

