## 6.1 Study Calendar

Period/ Procedure	Screening	Cycle 1		Cycle 2+	End of Treatment	Safety Follow- up	Safety Follow-up	Long Term Follow-up
Study Day/Visit Day	Day -28 to -1 unless otherwise noted	D1 (± 3d)	D15 (± 3d)	D1 (± 3 days)		30 days (± 7 days) post-last dose	100 days (± 14 days) post-last dose	Every 90 days  (± 30 days)
Study Treatment/Drug Administration								
Apalutamide			X					
Cetrelimab infusion		X		X				
Administrative Procedures								
Informed Consent	X							
Clinical Assessments								
Medical History	X							
Concurrent Medications	X	X	X	X				
Physical Exam 	X 	X 	X 	X 	X 			
Vital Signs (blood pressure and heart rate)	X	X	X	X	X			
AE assessment	X	X	X	X	X	X	X 	
ECOG/Karnofsky Performance Status	X	X	X	X	X			
Survival/Long-term Follow-up 								X
Laboratory Assessments								
Hematology 	X	X	X	X	X	X		
Chemistry 	X	X	X	X	X	X		
Thyroid Function Tests 	X	X		X	X			
Serum PSA	X	X		X	X			
Serum Total Testosterone	X							
Whole blood peripheral immune markers 		X		X 	X			

Period/ Procedure	Screening	Cycle 1		Cycle 2+	End of Treatment	Safety Follow- up	Safety Follow-up	Long Term Follow-Up
Study Day/Visit Day	Day -28 to -1 unless otherwise noted	D1 (± 3d)	D15 (± 3d)	D1 (± 3 days)		30 days (± 7 days) post-last dose	100 days (± 14 days) post-last dose	Every 90 days (± 30 days)
Isolation of peripheral blood mononuclear cells (PBMC)				X 	X 			
Circulating tumor cells 		X 		X 	X 			
Circulating tumor DNA 		X 		X 	X 			
Imaging Procedures								
CT Chest, Abdomen, and Pelvis 	X			X				
Bone scan 	X			X				
CT/MR brain 								
Tissue Collection/ Biopsy								
Tumor Tissue Collection 	X				X			
Skin biopsy for Grade ≥2 rash, if clinically indicated 					X 			

 Patients will be followed for overall survival every 90 days (+/- 30 days) from last dose of study treatment. Follow up will be conducted via chart review and/or telephone call.

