OPTIONAL: In the event that one or more standard of care skin biopsies are conducted, extra tissue may be collected for research (immune correlate assay to explore the mechanism of skin rash) only for patients who give optional consent for the extra tissue collection. Refer to the Lab Manual and Section 6.4.5 for additional information.

 PBMCs will be isolated from blood of patients experiencing Grade  $\geq 2$  rash (within 14 days of symptom onset when feasible) and from patients which have not experienced any Grade rash at end of treatment.

 Whole blood will be collected on C1D1 (pre-dose), C2D1 (pre-dose), C3D1 (pre-dose), and End of Treatment. Samples were stored at Epic Sciences for circulating tumor cell analysis, however, as of Amendment 1.8 dated 07-24-2023, Epic Sciences is no longer analyzing these samples. All remaining samples stored at Epic Sciences will be returned to UCSF and stored at the UCSF CTSI lab. Whole blood will continue to be collected and stored at the CTSI for future research..

 Plasma for circulating tumor DNA analysis including 5-hydroxymethyl cytosine (5-hmC) sequencing will be collected on C1D1 (pre-dose), C2D1 (pre-dose), C3D1 (pre-dose), and End of Treatment. Plasma will be sent to the [name] laboratory at UCSF.

 Height at screening only. Weight at each physical exam visit (patient will self-report if PE is during a telemedicine visit).

 On Cycle 1 Day 15 and the End of Treatment (EOT) visit, the physical exam may be done via a telemedicine visit. Other physical exams must be performed in-person. Vital signs (BP and heart rate) will be self-reported by the patient when the physical exam is a telemedicine visit.

 If AE assessment done at EOT visit, just needs to be done at 30-day Safety Follow-Up

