#### **6.3.4 30-day Safety Follow Up (+/- 7 days)**

- Clinical Assessments
  - AE assessment (may be performed via telephone)
- Laboratory Assessments
  - Hematology labs - CBC with differential and platelet count
  - Blood chemistry assessment, including: ALP, ALT/AST, total bilirubin, calcium, BUN, creatinine, potassium, sodium, chloride, bicarbonate

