#### **6.3.5 100-day Safety Follow-Up (+/- 14 days)**

- Clinical Assessments
  - AE assessment (may be performed via telephone; if AE assessment was done at EOT visit, 100-day Safety Follow-Up AE assessment not required)

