#### **6.3.6 Long Term/Survival Follow-up**

Patients will be followed for overall survival every 90 days (+/- 30 days) from last dose of study treatment, until death, withdrawal of consent, or the end of the study, whichever occurs first.

Follow up will be conducted via chart review and/or telephone call.

End of study is defined as three years after last dose of study drug.

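### The safety endpoint ends at treatment discontinuation although AEs are assessed 30 days later, and the 100-day AE assessment is waived by an end-of-treatment assessment due from everyone

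*Combined protocol and SAP*

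**What the plan says.** The first secondary endpoint in section 2.3 is the proportion of participants with treatment-related AEs, and its time frame is "From initiation of study treatment until treatment discontinuation". Section 7.2 starts the safety analyses at the first dose and gives no end. Section 8.3.3 describes the AE tables for this objective and gives no window.

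The protocol also plans AE collection after treatment. Section 3.6 states: "Participants will have safety follow up assessment 30 (+/- 7 days) and 100 days (+/- 14 days) following End of Treatment". The Abstract lists the same two time points: "Safety Follow up: 30 days Safety Follow-up: 100 days". Section 6.3.4 keeps the 30-day AE assessment for all, by telephone if wished.

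The 100-day assessment carries a condition. Section 6.3.5 says "if AE assessment was done at EOT visit, 100-day Safety Follow-Up AE assessment not required", and footnote 15 of the Study Calendar, attached to the 100-day AE cell, says "If AE assessment done at EOT visit, just needs to be done at 30-day Safety Follow-Up". The EOT AE assessment is listed without condition in section 6.3.3 and marked in the calendar.

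**The concern.** There are two separate faults. First, the endpoint's time frame closes before the protocol's own AE collection does, so data gathered at the 30-day visit on post-treatment onsets do not count in the endpoint. Second, the condition for skipping the 100-day assessment is one that every participant meets if the schedule is followed. An assessment at EOT cannot detect an event that begins later, so it is no substitute for a later one.

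Safety is the first secondary objective. Section 7.3.3.4 names immune-related reactions as the AEs of special interest for cetrelimab, and the third exploratory objective relates immune-related AEs to efficacy. Both uses depend on which AEs are looked for and which are counted. A restricted time frame can be widened at analysis; an assessment that was never made cannot be recovered.

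**Working it through.** The plan gives no figure to reproduce here. The check sets the passages side by side, with simple arithmetic on the visit windows.

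**Step 1. Where AE counting or scheduled assessment ends, in days after treatment**

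| Source | End point |
|---|---|
| 2.3, safety time frame | day 0 |
| 6.3.4, with the 100-day waiver applied | day 30 (30 − 7 = 23 to 30 + 7 = 37) |
| 3.6 as written | day 100 (100 − 14 = 86 to 100 + 14 = 114) |
| 7.2 and 8.3.3 | not stated |

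**Step 2. What section 2.3 excludes.** If onset date governs, an AE that began on treatment but was first recorded at day 30 still falls inside the time frame. What falls outside is a related AE with onset after discontinuation. It changes the proportion only in a patient who had no related AE on treatment.

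**Step 3. What the waiver removes.** The AE assessment is the only item at the 100-day visit in both section 6.3.5 and the calendar. With the EOT assessment due from everyone, the visit is empty by default. Only a participant who missed the EOT assessment still owes the 100-day one, so the longest scheduled follow-up goes to those with incomplete EOT data. The stretch without a scheduled AE assessment is:

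- nominal: 100 − 30 = 70 days
- shortest: 86 − 37 = 49 days
- longest: 114 − 23 = 91 days

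**Step 4. What remains after about day 30.** Section 6.3.6 provides a survival contact: "Patients will be followed for overall survival every 90 days (+/- 30 days) from last dose of study treatment". The first falls at 90 − 30 = 60 to 90 + 30 = 120 days. It is made by chart review and/or telephone, and the calendar marks no AE assessment for it. The other routes are event-driven: AEs of special interest (7.3.3.4), related deaths within 100 days of the last dose (7.3.7), and reporting to the industry partner (also 7.3.7).

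**Step 5. How the two faults interact.** While section 2.3 governs, the waiver does not change the endpoint, because onsets after discontinuation do not count anyway. The waiver affects what is known about late events, and it would affect the endpoint only once the time frame is extended past day 30.

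**Step 6. Scale.** With 24 treated patients, k patients whose first related AE starts after discontinuation move the proportion by k/24: 1/24 = 4.2, 2/24 = 8.3 and 3/24 = 12.5 percentage points. These values of k are illustrations; the documents give no basis for choosing one.

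**Step 7. Anchor.** Section 3.6 counts from End of Treatment. The calendar column reads "100 days (± 14 days) post-last dose". The EOT visit has no stated timing, and section 5.2 lets one drug continue after the other is stopped for an AE. The two counts need not coincide.

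**The case against.** The best reply is that the plan is stricter than the concern suggests. Section 2.3 is the only place that gives an end, section 7.2 gives the same start, and the section 8.3.3 text is the analysis of that very objective. A reader might infer that the three sections contradict one another. They do not: the silence of 7.2 and 8.3.3 is an omission, and an analyst who follows 2.3 has an answer. Collecting safety data beyond an endpoint's time frame is not in itself inconsistent either. All of that stands. What it does not remove is that the answer excludes post-treatment onsets which the protocol schedules a visit to find.

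On the waiver, the detailed schedule states its condition twice and consistently, and could be read as qualifying the general statements in the Abstract and section 3.6. But a condition met by everyone who follows the schedule cancels the visit; it does not qualify it.

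A reader might also infer that AEs after day 30 go unrecorded. The documents do not support this. The industry-partner provisions in section 7.3.7 cover all AEs following exposure with no stated end date, and serious AEs and AEs of special interest must be transmitted within 24 hours of awareness. Late immune-related reactions are therefore reportable once known. This limits the harm, but such reporting acts on events that come to light and is not scheduled ascertainment.

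Finally, the 100-day period in section 7.3.7 concerns only notification of related deaths, and the calendar's 100-day cell itself carries the waiver. Neither independently establishes a 100-day AE window. That also stands, and the fix leaves the choice to the sponsor.

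**Conclusion.** The point holds in two parts. The section 2.3 time frame omits related AEs with onset after discontinuation, including those recorded at the 30-day visit. The 100-day assessment stated in the Abstract and section 3.6 is cancelled by default, so scheduled AE assessment stops at about day 30. The anchor difference is real but minor.

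The direction is certain: the proportion under section 2.3 can only be equal to or lower than one that includes post-treatment follow-up. The size cannot be derived. It is tempting to take the 66.7% (142/213) related-AE rate for cetrelimab monotherapy in section 1.5 as an on-treatment rate, so that about a third of patients would remain at risk of a late first event. The documents do not support this: section 1.5 states no window for that figure, so it may already include post-treatment events, and it is not a rate for the combination. The 4.2-point step per patient assumes that all 24 patients are treated and that onset date decides whether an AE counts.

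The primary endpoint, the two-stage design and the cycle 1 safety rule in section 8.2 are unaffected. This should be corrected, but it does not threaten the trial's main conclusion.

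**What to change.** 1. In section 2.3, extend the safety time frame to cover the protocol's scheduled post-treatment safety follow-up, at minimum the 30-day visit data already collected. State the same window in sections 7.2 and 8.3.3, and say that onset date decides inclusion.
2. Reconcile the Abstract and section 3.6 with section 6.3.5 and footnote 15. Either remove the link to EOT, so that the 100-day AE assessment is not cancelled by an earlier one, or, if the visit is not intended, correct the Abstract, section 3.6 and the calendar.
3. Use one anchor throughout, defined as the last dose of whichever study drug is stopped last.
4. Tabulate separately AEs that start after new anti-cancer therapy, in line with the follow-up limit in section 7.3.5.

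Counting the 30-day data adds no data collection. Keeping the 100-day assessment costs at most 24 telephone contacts that the protocol already lists; the separate tabulation needs one flag in the data. The reported AE proportion may be higher, and attribution of late events is less certain, especially after new therapy.

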## 2.4 Exploratory (Correlative) Objectives

Exploratory Objectives	Endpoints
1. To explore the association between baseline metastatic tumor characteristics including t-SCNC, AR, RB1 loss, and immune response transcriptional signatures with clinical outcomes.	Association of specific gene and transcriptional gene signatures using RNA-seq and targeted next-gen DNA sequencing with composite response rate and PFS.
2. To evaluate objective response rate and median progression-free survival by irRECIST criteria.	Objective response rate and median PFS by irRECIST.
3. To evaluate the association between immune related adverse events (irAEs) and clinical efficacy outcomes.	Association between irAEs with efficacy endpoints including composite response rate, PSA50 response, and progression-free survival.
4. To evaluate the association between baseline and change from baseline in circulating T cell and myeloid cell subsets with clinical outcomes.	Association between baseline and fold change in circulating T cell and myeloid subsets by CyTOF with efficacy endpoints including composite response, PSA50 response, and progression-free survival.
5. To explore the mechanism of skin rash in patients receiving combination of apalutamide plus cetrelimab.	Infiltration of immune cells in skin biopsies performed in patients experiencing rash on study.
6. To explore the association between genomic and epigenomic features of circulating tumor DNA with clinical outcomes.	Association between genomic and epigenomic alterations in ctDNA with clinical outcomes.
7. To explore the association between circulating tumor cell (CTC) characteristics including heterogeneity, overall CTC count, and expression of markers of interest (AR, CD56, cytokeratin) with clinical outcomes.	Association between CTC characteristics with clinical outcomes.

## 3 Study Design

### 3.1 Characteristics

This is a phase 2, single arm, Simon's two-stage evaluation of the combination of apalutamide plus cetrelimab in patients with mCRPC and histologic and/or genomic evidence of treatment-emergent small cell neuroendocrine prostate cancer who have previously progressed on at least one prior androgen signaling inhibitor. The primary study endpoint is composite response rate as defined by PSA50 response and/or objective response by RECIST 1.1 criteria.

A planned interim safety and efficacy analysis is planned after 14 patients are treated (see Section 8).

[figure not shown]

Figure 3.1 Study Schema

### 3.2 Sample Size

A total of 24 patients will be enrolled over an accrual period of approximately 18 months.

### 3.3 Eligibility Criteria

Patients must have screening procedures performed prior to Cycle 1, Day 1 of treatment and must meet all inclusion and exclusion criteria. In addition, the patient must be thoroughly informed about all aspects of the study, including study visit schedule, required evaluations, and all regulatory requirements for informed consent. The written informed consent must be obtained from the patient prior to enrollment. The following criteria apply to all patients enrolled onto the study unless otherwise specified.

#### 3.3.1 Inclusion Criteria

1. Participants must have histologically confirmed prostate adenocarcinoma at the time of diagnosis, with subsequent development of metastatic castration-resistant prostate cancer. Prostate adenocarcinoma with neuroendocrine features (e.g. positive chromogranin and/or synaptophysin expression by IHC) is allowed.
2. Evidence of disease progression (PD) by PSA and/or radiographic progression by PCWG3 criteria at the time of study entry.
3. Prior progression on at least one androgen signaling inhibitor (e.g. abiraterone acetate, apalutamide, enzalutamide, darolutamide). Treatment with prior androgen signaling inhibitor may have been initiated in either the CSPC and/or CRPC setting.
4. Patients must be evaluable for the primary endpoint of composite response and must have either serum PSA > 2 ng/mL during Screening and/or measurable disease by RECIST 1.1 criteria.

5. Participants must have clinicogenomic evidence of treatment emergent small cell neuroendocrine prostate cancer as defined by one or more of the following:
  - i. Histologic evidence of small cell neuroendocrine prostate cancer on evaluation of CRPC tissue by centralized pathology review  
and/or
  - ii. Presence of loss-of-function mutation or deletion of *RB1* on a CLIA-approved genomic-sequencing platform. Either monoallelic or biallelic mutations in *RB1* are allowed.
6. No more than one prior line of taxane-based chemotherapy administered in the mCRPC setting. Chemotherapy administered in the castration-sensitive setting does not count towards this limit. Prior carboplatin is allowed and does not count as an additional line of therapy when given in conjunction with taxane.
7. Castrate level of serum testosterone at study entry (<50 ng/dL). Patients without prior bilateral orchiectomy are required to remain on LHRH analogue treatment for duration of study.
8. No other systemic anti-cancer therapies administered other than LHRH analogue within 14 days or, 5 half-lives, whichever is shorter, prior to initiation of study treatment. AEs related to prior anti-cancer treatment must have recovered to Grade  $\leq 1$  with the exception of any grade alopecia and Grade  $\leq 2$  neuropathy.
  - b. Patients receiving apalutamide prior to study entry may continue treatment at their current apalutamide dose level without requirement for wash-out period.
9. Age  $\geq 18$  years
10. ECOG performance status  $\leq 1$  (Karnofsky performance status  $\geq 70\%$ , see Appendix 1)
11. Demonstrates adequate organ function as defined below:

Adequate bone marrow function:

Absolute neutrophil count	$\geq 1,500/\text{mcL}$
Platelets	$\geq 100,000/\text{mcL}$
Hemoglobin	$\geq 9.0 \text{ g/dL}$

Adequate hepatic function:

Total bilirubin	$\leq 1.5 \times$ institutional upper limit of normal, unless elevated due to Gilbert's syndrome and direct bilirubin is within normal limits
AST (SGOT)	$\leq 3 \times$ institutional upper limit of normal ( $\leq 5 \times$ ULN in presence of liver metastases)
ALT (SGPT)	$\leq 3 \times$ institutional upper limit of normal ( $\leq 5 \times$ ULN in presence of liver metastases)

Adequate renal function:

Serum creatinine	$\leq 1.5 \times$ institutional upper limit of normal
------------------	---

OR

Calculated creatinine clearance      GFR  $\geq$  30 mL/min/1.73 m^2, calculated using the CKD-EPI equation

12. Ability to understand a written informed consent document, and the willingness to sign it.
13. Patients must agree to use adequate contraception and to not donate sperm prior to the study, for the duration of study participation, and 5 months after last administration of study treatment. Adequate contraception includes (see Appendix 3 for more detail):
  - c. Patients who are sexually active should consider their female partner to be of childbearing potential if she has experienced menarche and is not postmenopausal (defined as amenorrhea  $>$  24 consecutive months) or has not undergone successful surgical sterilization.
  - d. Even participants who have undergone vasectomy should still use acceptable method of contraception.
  - e. Acceptable methods of contraception include hormonal combined (estrogen + progesterone) or progesterone only given orally, injected or implanted; IUD, IUS, tubal ligation, vasectomy and complete sexual abstinence.
14. Patients must be willing to undergo metastatic tumor biopsy during Screening if no biopsy has previously been done. If no metastatic lesion is safely accessible to tumor biopsy, this requirement will be waived. Bone or soft tissue lesion is allowed, but soft tissue will be prioritized. If a patient has archival tissue obtained within 90 days of C1D1 the requirement for fresh tumor biopsy will be waived.

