### 5.2.1 Retreatment Criteria for Cetrelimab and Apalutamide

**Table 5.2 Retreatment Criteria**

Adverse Event	Requirements before each study agent administration
Absolute neutrophil count	$\geq 1.0 \times 10^9/L$
Platelet count	$\geq 50 \times 10^9/L$ with or without platelet transfusions and/or growth factors
Hemoglobin	$\geq 8.0 \text{ g/dL}$ with or without transfusion, growth factors, or both
Fasting glucose, if prompted by HbA1c	$\leq 250 \text{ mg/dL}$
Hyperthyroidism	Grade $\leq 2$
AST and ALT	$\leq 3 \times \text{ULN}$ ( $\leq 5 \times \text{ULN}$ for patients with liver metastases)
Total bilirubin	$\leq 1.5 \times \text{ULN}$
Rash	Grade $\leq 2$
Other clinically significant toxicity 	Recovery to Grade $\leq 1$ or baseline

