### 5.2.2 Dose Delay for Cetrelimab

Dose reduction of cetrelimab is not permitted. Treatment delay of cetrelimab is required until re-treatment criteria are met (Table 5.2) and for any of the following AEs:

- Grade 2 pneumonitis (recurrent Grade 2 or Grade  $\geq$  3 pneumonitis, cetrelimab must be permanently discontinued)
- Grade 2 or 3 diarrhea or colitis
- Grade 2 nephritis with creatinine  $>$  1.5 – 3 x ULN
- Grade 2 or 3 creatinine elevation
- Grade 2 elevation in AST or ALT except for patients with liver metastases at baseline, or total bilirubin 1.5 – 3 x ULN
- Grade 2 toxicity related to treatment with cetrelimab that is intolerable or persistent (lasts  $>$  28 days)
- Symptomatic endocrinopathies (hypothyroidism, hyperthyroidism, hypophysitis, adrenal insufficiency diabetes)
- Grade 3 rash
- Other Grade 3 treatment related toxicity assessed as related to cetrelimab

If a cetrelimab dose must be delayed by more than 2 weeks, administration should continue at the next planned dosing date and the dose will be considered a missed dose.

Study treatment with cetrelimab should be permanently discontinued for any of the following:

- The investigator believes that for treatment-emergent toxicity it is in the best interest of the subject to discontinue study treatment
- Grade 4 toxicities except for:
  - endocrinopathies that are controlled with replacement hormones
  - Grade 4 hematologic toxicities that resolve in less than 7 days may not result in study treatment discontinuation at the discretion of the treating physician.
- Grade 2 or 3 irAEs that persist despite treatment modifications or corticosteroid dosing cannot be reduced to  $\leq$  10 mg prednisone or equivalent per day within 12 weeks
- A treatment-related AE does not resolve to Grade  $\leq$  1 within 12 weeks of the last dose of study drug unless otherwise agreed to by the sponsor medical monitor and the investigator based on evidence of clinical benefit
- Any non-hematological treatment-related event occurs a second time at Grade  $\geq$  3 severity
- Grade  $\geq$  3 (or recurrent Grade 2) pneumonitis
- Grade  $\geq$  3 nephritis with creatinine  $\geq$  3xULN
- Grade  $\geq$  3 elevation of AST or ALT  $>$  5xULN or total bilirubin  $>$  3xULN
  - For subjects with baseline Grade 2 elevation of AST or ALT due to liver metastasis, only Grade  $\geq$  3 elevations that are  $\geq$  50% of baseline for  $\geq$  7 days will require discontinuation of study treatment

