- Grade  $\geq$  3 infusion-related reactions (IRRs)
- Immune-mediated encephalitis

Once a subject discontinues treatment, the subject may not be retreated with the study drug.

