### 5.2.3 Dose Modification for Apalutamide

Apalutamide dose reductions due to toxicities other than rash are described in the table immediately below. Management of rash, including dose reductions, is described in Section 5.4. Apalutamide dose may be reduced as follows: first dose-level reduction to 180 mg/day, second dose-level reduction to 120 mg/day. If further dose reduction is required, apalutamide should be discontinued.

Event	Clinically Significant Hematologic and Non-Hematologic AEs Deemed Related to Apalutamide
Grade 1 or 2	Dose delay up to 4 weeks or dose reduction at the discretion of the investigator.
Grade 3	Hold apalutamide until AE has improved to Grade $\leq 1$ or baseline and resume with a dose reduction. If apalutamide cannot be restarted within 4 weeks, it should be discontinued. Discontinue for Grade 3 toxicity that recurs after 2 dose reductions.
Grade 4	Permanently discontinue apalutamide.

Doses re-escalation back to the previous dose level may be permitted upon discretion of the Principal Investigator.

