### 6.5.2 Acceptable Concomitant Medications/Supportive Care

Participants should receive appropriate supportive care measures as deemed necessary by the treating investigator. Suggested supportive care measures for the management of AEs with potential immunologic etiology are outlined along with the dose modification guidelines. Where appropriate, these guidelines include the use of oral or IV treatment with corticosteroids, as well as additional anti-inflammatory agents if symptoms do not improve with administration of corticosteroids. Note that several courses of steroid tapering may be necessary as symptoms may worsen when the steroid dose is decreased. For each disorder, attempts should be made to rule out other causes such as metastatic disease or bacterial or viral infection, which might require additional supportive care. The treatment guidelines are intended to be applied when the Investigator determines the events to be related to cetrelimab.

Note: If after the evaluation of the event, it is determined not to be related to cetrelimab, the Investigator does not need to follow the treatment guidance. Refer to guidelines regarding dose modification and supportive care.

Patients are recommended to use bone-modifying agents (e.g. denosumab, zoledronic acid) during Screening and Treatment phases of the study to decrease risk of fracture.

LHRH analogues are required during Study Treatment except for patients with history of bilateral orchiectomy.

Patients are recommended to taper off prednisone prior to study enrollment but are allowed to take doses up to  $\leq$  10 mg daily prednisone or prednisone equivalent. Doses of steroids higher than prednisone 10 mg daily (or prednisone equivalent) are permitted only for the treatment of immune related AEs.

Treatment with antiemetic therapy will be permitted, if clinically indicated.

Treatment with filgrastim or other colony stimulating factors will be permitted for Grade 3 or higher hematologic toxicity as per Package Insert but may not be used prophylactically.

Treatment required for care of complications/AEs arising from the cancer and/or treatment will be permitted.

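### The Gilbert's syndrome waiver of the total bilirubin limit at entry is not carried into the Table 5.2 dosing requirement or the cetrelimab bilirubin rules in section 5.2.2

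*Combined protocol and SAP*

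**What the plan says.** **Entry.** Inclusion criterion 11 in section 3.3.1 sets total bilirubin at no more than 1.5 x ULN, "unless elevated due to Gilbert's syndrome and direct bilirubin is within normal limits". No ceiling is given for patients who use this route. Gilbert's syndrome is mentioned nowhere else in the document.

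**Dosing, both agents.** Table 5.2 in section 5.2.1 lists limits under the column header "Requirements before each study agent administration". Its bilirubin row is 1.5 x ULN or below, with no exception.

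**Cetrelimab delay.** Section 5.2.2 states: "Treatment delay of cetrelimab is required until re-treatment criteria are met (Table 5.2) and for any of the following AEs". One listed item is Grade 2 AST or ALT elevation "except for patients with liver metastases at baseline, or total bilirubin" of 1.5 to 3 x ULN. The exception in that item belongs to the transaminases.

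**Cetrelimab stop.** The permanent discontinuation list in section 5.2.2 has one item that joins a Grade 3 or higher transaminase elevation above 5 x ULN with total bilirubin above 3 x ULN. Its sub-item opens "For subjects with baseline Grade 2 elevation of AST or ALT due to liver metastasis" and does not mention bilirubin. The section ends: "Once a subject discontinues treatment, the subject may not be retreated with the study drug".

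**Monitoring.** The chemistry panel in the Study Calendar (section 6.1, footnote 3) lists total bilirubin but not direct bilirubin.

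**The concern.** A protocol that deliberately admits a patient with a benign, stable laboratory value should not then withhold drug because of that same value. On the literal text it does. Cetrelimab delay is mandatory until Table 5.2 is met, and a constitutional elevation may never meet it. Under section 5.2.2 a delay beyond 2 weeks becomes a missed dose. Under section 5.2 an interruption beyond 28 days may end only if the patient is benefiting and the Principal Investigator approves.

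If the investigator instead treats the value as outside these rules, the patient is dosed on judgment. Nothing then says when the allowance ends, and direct bilirubin, the quantity that justified the waiver, is not on the scheduled panel. Bilirubin can also rise on treatment: section 1.5 reports Grade 3 or higher hyperbilirubinemia in 1.9% of 213 cetrelimab monotherapy subjects. A new rise in a Gilbert's patient needs a rule that can tell it apart from his usual level.

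**Working it through.** There is no plan figure to reproduce. The check sets the rules side by side.

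**Step 1. Entry limit against dosing limit.** Five rows of Table 5.2 also have a limit in inclusion criterion 11. Entry counts per mcL are converted to 10^9/L (1,500/mcL = 1.5; 100,000/mcL = 100).

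| Item | Entry (3.3.1) | Dosing (Table 5.2) | Dosing relative to entry |
|---|---|---|---|
| Neutrophils, 10^9/L | at least 1.5 | at least 1.0 | looser |
| Platelets, 10^9/L | at least 100 | at least 50 | looser |
| Hemoglobin, g/dL | at least 9.0 | at least 8.0 | looser |
| AST/ALT, x ULN | at most 3 (5 with liver metastases) | the same | equal |
| Total bilirubin, x ULN | at most 1.5; waived for Gilbert's | at most 1.5 for all | stricter for Gilbert's |

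Three rows are looser, one is equal and one is stricter. Within Table 5.2, bilirubin is the only row that an eligible patient can fail on his entry value.

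**Step 2. Exceptions carried forward.** Across Table 5.2, the delay rule and the stop rule, AST/ALT has a liver-metastasis exception in 3 of 3 places. Bilirubin has a Gilbert's exception in 0 of 3. This pattern looks more like an oversight than a decision.

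**Step 3. A worked patient (illustrative value).** Total bilirubin is 2 x ULN from Gilbert's syndrome, with normal direct bilirubin.
- Entry: 2 > 1.5, but the waiver applies, so he is eligible.
- Table 5.2: 2 > 1.5, so the requirement fails for both agents. If the word retreatment is taken to leave out Cycle 1 Day 1, the failure moves to Cycle 2 Day 1.
- Section 5.2.2 delay: 1.5 < 2 < 3, so he is inside the cetrelimab delay band.

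At a value above 3 x ULN, which the waiver does not rule out, he may also meet the stop rule. This depends on whether the Grade 3 or higher qualifier at the start of that item also governs bilirubin.

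**Step 4. Search for a rescue clause.** Table 5.2 does allow return to baseline, but only in its catch-all row for other toxicity, not in the bilirubin row.

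**Step 5. Context figure.** 0.019 x 213 = 4.05, so about 4 monotherapy subjects had Grade 3 or higher hyperbilirubinemia. These are treatment-emergent events of any cause, and nothing links them to Gilbert's syndrome. The figure shows only that on-treatment rises occur.

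**The case against.** The best defence is that these are adverse-event rules. Table 5.2 labels its first column as adverse events and sits under toxicity management. The delay list is likewise introduced as a list of AEs, and section 7.3.1 defines an AE by its association in time with drug use. A stable value that predates treatment does not plainly fit. This stands in part: it makes the text ambiguous. It does not remove the literal conflict, because the requirement applies before every administration and the delay sentence separately demands that Table 5.2 be met.

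Other provisions soften the effect without amending the threshold:
- Section 6.5.2 says "The treatment guidelines are intended to be applied when the Investigator determines the events to be related to cetrelimab", but it sits under supportive care.
- For apalutamide the conflict comes only from Table 5.2. The section 5.2.3 table is limited to "Clinically Significant Hematologic and Non-Hematologic AEs Deemed Related to Apalutamide", and it ends a Grade 3 hold at Grade 1 or baseline.
- Exclusion 20 lets the investigator screen out a patient whose laboratory abnormality would interfere with participation. That is discretionary.
- Section 7.3.5 allows re-challenge for selected AEs, but section 5.2.2 bars retreatment after discontinuation.

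Two stronger readings are tempting. A reader might infer that every Gilbert's patient above 3 x ULN must stop cetrelimab permanently. That rests on one parse of the stop rule. If the grade qualifier governs bilirubin too, the answer depends on how CTCAE 5.0 grades a pre-existing value, which the documents do not reproduce. A reader might also infer that bilirubin is the only entry and dosing mismatch. It is the only one within Table 5.2. However, inclusion criterion 11 also admits a patient with creatinine above 1.5 x ULN through the GFR route, while section 5.2.2 delays cetrelimab for Grade 2 or 3 creatinine elevation.

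**Conclusion.** The point holds as a drafting conflict in a safety rule. On the literal text, the Table 5.2 row and the cetrelimab delay rule withhold drug from a patient whom inclusion criterion 11 chose to admit. On the adverse-event reading he is treated, but with no stated limit. The permanent stop is a possible further consequence, not an established one.

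The size is small. The documents give no frequency for Gilbert's syndrome, so the number affected among 24 patients is unknown and may be zero. A reader might infer that held doses would pull down the composite response rate, since section 8.3.1 keeps such a patient in the primary analysis population. The documents give no basis for sizing that, and the two-stage design and its error rates are untouched. The conclusion assumes only that a Gilbert's patient above 1.5 x ULN is enrolled. It is worth correcting because the repair is cheap and the rule concerns patient safety.

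**What to change.** In the Table 5.2 bilirubin row and in both bilirubin rules of section 5.2.2, add a clause for patients who enter on the Gilbert's waiver. For them, the limits should apply to:
- direct bilirubin, which must stay within normal limits; and
- total bilirubin relative to the patient's own baseline, with a hold and a stop each at a stated multiple of that baseline. The documents give no basis for choosing the multiples, so the sponsor should set them.

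A plain Gilbert's exception would be shorter but less safe. It would remove every total bilirubin limit while direct bilirubin is normal, so a new, mainly indirect rise would trigger nothing. Under the two-part rule, a new rise of either type still leads to a hold or stop.

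Add direct bilirubin to the Day 1 chemistry of each cycle for these patients only. In the same amendment, state whether the Grade 3 or higher qualifier in the stop rule covers bilirubin.

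The cost is a few lines in one amendment and one routine laboratory test in the patients concerned. Eligibility, sample size, error rates and analysis stay as they are.
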